9. INVESTIGATIONAL MEDICINAL PRODUCT (IMP)INVESTIGATIONAL MEDICINAL PRODUCT (IMP)

9.1. Cytisine 1.5 mg Film-Coated Tablets

Cytisine (cytisinicline) will be supplied by the Sponsor. The cytisine drug product is formulated as a compressed film-coated tablet containing 1.5 mg cytisine in a single tablet. Each tablet is composed of cytisine active substance (as the base) supplied by [REDACTED]

9.2. Placebo Tablets

Placebo tablets will contain the same excipients as in the cytisine tablet formulation plus an additional [REDACTED] to match final weight of the cytisine tablet. Placebo tablets will be identical in size, shape, color, and packaging to preserve the double-blind study design.

9.3. Receipt and Storage

A clinical supplies management vendor will label, package, and distribute study drug to the sites.

Drug supply will be managed via an IRT program to maintain predetermined stock levels at the sites and/or handle resupply using site initiated requests. Upon receipt, details of study drug supplied shall be documented using the IRT and/or internal site login procedures.

The study drug shall be stored in a secure, temperature controlled location and only dispensed by suitably trained staff.

9.4. Administration

Study drug will be supplied as compressed tablets in folded blister packs. The folded blister packaging will be designed for specific days of treatment and for the two different dosing schedules. Thus, the commercial titration schedule will have different blister packaging compared to the tid schedule. At specific clinic visits, a series of blister packets will be given to subjects for dosing over a few days and are to be returned at subsequent clinic visits with the last blister packets returned upon completion of treatment.

Tablets should be swallowed whole with water.

9.5. Return/Destruction

All unused study drug should be destroyed by the sites unless a prearranged return to depot or Sponsor is necessary.

9.6. Method of Assigning Subjects to Arms

Subjects will be allocated to arms according to a predetermined randomization schedule and randomly assigned (2:1) to active vs. placebo once all screening procedures are completed and verified. Randomization will be stratified by BMI class (18.5 to <25 kg/m²; 25 to <30 kg/m²; 30 to <35 kg/m²).

Subjects will be assigned a unique study identification (I.D.) number upon signing the informed consent form, prior to conducting any protocol-specified procedures by the site. The study I.D. number will consist of 2 parts. The first part identifies the site (3 digits) and the second part identifies the subject (3 digits). Subject numbers will be assigned sequentially from 101 (i.e. 101, 102, etc.). Study drug assignment will occur via IRT. The IRT system will identify what study drug packet should be used via a randomly-assigned number printed on the packet so that treatment assignment blind can be maintained. The site will label the assigned packet with the subject's study I.D. number and include both in the applicable source documents (i.e. drug accountability log).

For treatment compliance, study drug will be packaged into folded packets covering treatment segments that will align with clinic visits. Treatment segment packets will be distributed, returned and reviewed at each scheduled site visit for ongoing accountability (see Section 9.8).

The clinical research staff will record study drug (tablet) administration and all related information on the applicable source documents, to allow investigational product accountability and evaluation of subject compliance.

9.7. Study Drug Dosing Schedule

All subjects will receive 2 tablets for each dose. According to randomization, subjects will receive study drug as follows:

Specified Tablets	Arm A or Arm D (1.5 mg Dose)	Arm B or Arm E (3.0 mg Dose)	Arm C or Arm F (Placebo)
Cytisine 1.5 mg tablets	1 tablet	2 tablets	-
Placebo tablets	1 tablet	-	2 tablets

For 25-day titration schedule, study drug will be administered according to the following treatment day schedule:

Treatment Day	Daily Administration
1 ^a -3	6 times daily
4-12	5 times daily
13-16	4 times daily
17-20	3 times daily
21-24	2 times daily
25	1 time only

^aInitial treatment day 1 for the 25-day Treatment Period must start on the day after randomization.

For the tid schedule, study drug will be administered according to the following treatment schedule:

Treatment Day	Daily Administration
1 ^a -20	3 times daily
21-24	2 times daily
25	1 time only

^aInitial treatment day 1 for the 25-day Treatment Period must start on the day after randomization.

9.8. Accountability

The pharmacist or pharmacist designee will maintain records of study drug receipt at the trial site, inventory at the site, dispensing for each subject, and any destruction or possible return of unused doses to the site for investigational product accountability.

To facilitate accurate compliance and accountability, study drug for each subject will be configured into 9 medication packs, regardless of the 25-day treatment scheduled assignment (commercial titration schedule or simplified tid schedule). Each of the 9 packs will contain the correct number of tablets for the days of treatment as follows:

Pack Number	Days of Treatment
1	1-2
2	3-4
3	5-7
4	8-10
5	11-13
6	14-15
7	16-17
8	18-21
9	22-25

Clinic staff will distribute and collect packs as the subject progresses through the clinic visits and will conduct ongoing accountability during each clinic visit by reviewing each subject's dosing timing and associated blister packs. Used packs will be retained so that the Sponsor's monitoring staff can verify accountability records.

Upon completion of the study and final accountability monitoring, all the investigational product that has not been used and all the empty containers of the used investigational product at the sites will be destroyed or returned to the depot or Sponsor.

10. PREVIOUS AND CONCOMITANT MEDICATIONS

All subjects will continue to receive any existing prescription medication. Every effort should be made to ensure that the regimen of existing medications remain stable during the study.

At the discretion of the Investigator, the use of non-study drug medications (either prescription or over-the-counter) may be given if clinically-indicated during the study. Full details of any new medications must be recorded in the subject's Case Report Form (CRF).

All concomitant medication(s) taken during the trial and any changes (additions, deletions, dose changes) must be recorded in the CRF. This must include any use of non-cigarette nicotine products.

11. TREATMENT COMPLIANCE

Treatment compliance will be monitored during the 25 day Treatment Period via review of dosing timing and drug accountability. Subjects will have a daily diary that will record the number of tablets taken and time taken. Subjects will be instructed to bring their medication packs (blister packs) to each clinic visit so that clinic staff can reconcile against the diary, recording the number of tablets taken and the number of missed tablets. In addition, a text messaging system will be implemented that will provide each subject with reminder texts corresponding to the approximate time of dosing.

12. STUDY PROCEDURES

After providing signed informed consent, all subjects will be evaluated for inclusion in the study within a 28 day Screening Period. Subjects who meet inclusion criteria will be required to provide a quit date that must be 5-7 days after the start of treatment and agree to initiating study treatment the day after randomization. Both planned quit and treatment start dates must be documented to confirm inclusion. Once all eligibility criteria are confirmed, randomization can occur. Study Day 1 will be defined as the first day of treatment. Subjects will complete a clinic visit on Day 2, 3, 6, 12, 16, 20 (during treatment), Day 27 (End-of-Treatment [EOT] visit), and again at the Week 5, 6, 7 and 8 visits.

12.1. Procedure Schedule

Table 10 provides a summary of required study evaluations. Refer to Section 12.2 for a detailed description of each study visit. Screening evaluations are to occur within a 28 day interval from initiation of screening evaluations to randomization. Day 1 will be defined as the first day of treatment. Subjects must initiate study treatment the day after randomization, such that study treatment is initiated prior to the quit date, which must be planned within 5-7 days after start of treatment. Both the planned treatment start date and the agreed-upon quit date must be documented at the time of randomization within the source documents and CRF.

Table 10: Schedule of Study Procedures

Study Assessment	Screening Period (Day-28 to Rand)		Randomization	Treatment Period Day 1 through Day 25									Follow-up Assessment Period ¹ (± 3 Days)			
	SV 1	SV 2 ²		Day 0	Day 1 ³	Day 2	Day 3	Day 6 (±1 Day)	Day 12 (±1 Day)	Day 16 (±1 Day)	Day 20 (±1 Day)	Day 27 EOT (±2 Days)	Week 5	Week 6	Week 7	Week 8
Informed Consent	•															
Inclusion/Exclusion	•															
Demographics	•															
Medical and Psychiatric History	•															
SBQ-R questionnaire	•															•
Physical Exam	• ⁴															
Smoking History	• ⁵	• ⁵														
Urine Pregnancy Test for all Females ⁶	•															
Drugs of Abuse Screen ^{6,7}	•															
Vital Signs including Weight	• ⁸		•		•	•	•	•	•	•	•	•	•	•	•	•
Hematology and Chemistry ⁶	•				•	•	•	•	•	•	•	•				•
12-lead ECG	•								•			•				
Concomitant Medications	•	•	•	•	•	•	•	•	•	•	•	•	•	•	•	•
Quit Date Set and Treatment Day 1 Scheduled		•														
Review Diary Completion Instructions	• ⁵		•													
Review Diary for Number of Cigarettes Smoked		• ⁵			•	•	•	•	•	•	•					
Adverse Event Reporting	•	•	•	•	•	•	•	•	•	•	•	•	•	•	•	•
Study Drug Distribution, Accountability and Collection			•		•	•	•	•	•	•	•					

Study Assessment	Screening Period (Day-28 to Rand)		Randomization	Treatment Period Day 1 through Day 25									Follow-up Assessment Period ¹ (± 3 Days)				
	Visit	SV 1		SV 2 ²	Day 0	Day 1 ³	Day 2	Day 3	Day 6 (±1 Day)	Day 12 (±1 Day)	Day 16 (±1 Day)	Day 20 (±1 Day)	Day 27 EOT (±2 Days)	Week 5	Week 6	Week 7	Week 8
Behavioral Support			• ⁹	•		•	•	•	•	•	•	•	•	•	•	•	•
Fagerström Test of Nicotine Dependence				•													
Self-Efficacy Questionnaire				•													
Craving Questionnaire				•		•	•	•	•	•	•	•	•	•	•	•	•
HADS Questionnaire		•							•			•					•
Alcohol Use Questionnaire				•													•
Smoking Cessation Status													•	•	•	•	•
Expired CO		•		•								•	•	•	•	•	•
Plasma Cotinine ⁶		• ¹⁰										•					•

¹Once study drug dosing has been completed and the End-of-Treatment visit has occurred at Week 4 (Day 25-27 post-randomization), smoking cessation status will be performed weekly during the Follow-up Assessment Period at Week 5 through to Week 8 post-randomization. Smoking cessation status at each visit from Week 5 through Week 8 will be defined by self-report of no cigarette smoking and CO levels. Cigarette smoking for the past 7 days as well as from the last clinic visit will be recorded.

²Randomization *may* occur at the SV2 visit IF subject can commit to a quit date that allows start of treatment the following day. In such cases all Day 0 (Randomization) procedures must be completed at the SV2 clinic visit.

³Clinic will telephone each subject towards the end of Day 1 (first day of treatment) to make sure subject has taken medication according to dosing schedule, answer any questions, assess for adverse events and any concomitant medications and confirm the Day 2 clinic appointment.

⁴Physical exam may be conducted at either the SV1 or the SV2.

⁵Number of cigarettes smoked daily will be recorded in a 7-day diary to be completed by the subject between SV1 and SV2. Adequate completion of the 7-day screening diary with an average of at least 10 cigarettes smoked per day is required for inclusion into the study.

⁶Urine pregnancy test kits supplied to site by central laboratory. All other testing performed by a central laboratory.

⁷Drugs of abuse to include at a minimum amphetamines, methamphetamines, barbiturates, benzodiazepines, cocaine, ecstasy, opiates, and phencyclidine.

⁸To include height at screening for BMI calculations (required for stratification).

⁹Setting the quit date and plan is to be considered the first behavioral support counseling session.

¹⁰ Plasma sample will be collected at SV1 and stored on all subjects. Only samples from randomized subjects will be tested for 3-OH cotinine and cotinine levels to determine the nicotine metabolite ratio (NMR) at baseline.

12.2. Detailed Description of Study Visits

12.2.1. Screening Phase

Screening assessments used to evaluate inclusion and exclusion criteria will occur over a 28 day period prior to randomization and must include a minimum of 2 clinic visits.

Screening (Day 28 to Randomization Day 1)

Study procedures include:

Screening Visit #1

1. Written informed consent obtained.
2. Demographic data.
3. Medical and psychiatric history. Suicidal ideation is to be determined and documented via administration and assessment of the SBQ-R questionnaire ([Appendix 1](#)). Depression is to be assessed via administration of the HADS questionnaire ([Appendix 5](#)).
4. Physical examination.
5. Document any existing adverse events.
6. Concomitant medications.
7. Review of smoking history, to include year started smoking, information about previous quit attempts, and average number of cigarettes smoked per day over the past 30 days. Provide diary instructions to capture number of cigarettes smoked for 7 consecutive days. This diary will be reviewed at Screening Visit #2 to verify that Inclusion #2 is met (averaging at least 10 cigarettes per day over a 7 day period).
8. Expired CO.
9. Vital signs, including weight and height.
10. Urine pregnancy for all female subjects.
11. Drugs of abuse screen.
12. Hematology and serum chemistry testing. An additional plasma sample will be stored for all subjects. Only samples from randomized subjects will be tested for 3-OH cotinine and cotinine levels to determine the nicotine metabolite ratio (NMR).
13. 12-lead ECG.
14. Review all inclusion and exclusion criteria and if satisfied, schedule Screening Visit #2.

Screening Visit #2

1. During the Screening Visit #2 document any existing adverse events and concomitant medications. **Note:** Subjects must have adequately completed the 7-day daily smoking diary and have reported smoking an average of at least 10 cigarettes on 7 consecutive days to be eligible for inclusion into the study.

2. Each subject to provide their quit date, which must be 5-7 days after randomization (Treatment Day 5, 6 or 7) and the quit date must be documented. Setting a quit date and plan will be considered as the initial behavioral support session with the subject. The quit date will then determine the date for randomization. If a subject can commit to a quit date that allows for treatment to start the following day, the Screening Visit #2 may be treated as Day 0 and the subject can be randomized. In such cases, all procedures outlined in (Section 12.2.2) must be completed.

12.2.2. Randomization

Randomization (Day 0)

Randomization must occur 5-7 days prior to the agreed upon quit date so that the actual quit date falls on Treatment Day 5, 6 or 7. All other screening evaluations must be completed within 28 days prior to the Randomization Day. Study treatment must start on the day after randomization.

Study procedures include:

1. Update concomitant medication(s).
2. Document any existing adverse event(s).
3. Vital signs, including weight.
4. Expired CO.

Upon completion of all procedures and final confirmation of eligibility, complete the following:

1. Subject to complete the following questionnaires:
 - a. Fagerström Test for Nicotine Dependence ([Appendix 2](#)).
 - b. Smoking Self-Efficacy questionnaire (SEQ-12) ([Appendix 3](#)).
 - c. Short Form of the Tobacco Craving questionnaire ([Appendix 4](#)).
 - d. HADS questionnaire ([Appendix 5](#)).
 - e. Alcohol Use questionnaire ([Appendix 6](#)).
2. Provide subject with behavioral support information that includes counseling ([Appendix 7](#)). NOTE: it should be stressed to subjects that even if they are smoking less during the study treatment, they must maintain their dosing schedule throughout the Treatment Period.
3. Randomize according to a pre-determined, blinded, randomization schedule (see Section [7.5](#)).
4. Provide study treatment medication packs #1 and #2, which contain tablets required for Days 1-2 and Days 3-4. Enter actual treatment dates on the packs next to the dosing day designation in the space provided. Review the layout and dosing instructions printed on the medication packs which cover dosing requirements, timing of study drug administration and how to remove individual tablets from the blister pack. Instruct subject that any/all packs must be brought back to the clinic and should never be thrown away.
5. Develop an appointment schedule that includes dates and times for each required clinic visit during the trial, providing copy to the subject.
6. Provide diary instructions.

7. Schedule a time on the following day (day 1 of treatment, late in the day) when clinic will contact subject to assess compliance, any possible adverse events and any changes/additions in concomitant medications.
8. Remind subject of appointment time for Day 2 clinic visit.

12.2.3. Treatment Period

Treatment Day 1

All subjects must begin treatment on the morning of Day 1 and record all dosing in a diary.

Clinic to contact subject via telephone call in afternoon or evening of Treatment Day 1 to:

1. Verify subject is taking treatment according to their assigned dose schedule, review compliance requirements and answer any questions.
2. Verify subject is recording number of cigarettes smoked in past 24 hours in the diary (to be recorded at the same time each day).
3. Ask subject if any adverse events have occurred and/or any changes in concomitant medications.
4. Remind subject of their appointment time for the following day and that they must bring with them all study medication packs.

Treatment Day 2

1. Subject to complete the short form of the Tobacco Craving questionnaire ([Appendix 4](#)).
2. Review diary to verify dosing up to time of visit. Review number of cigarettes smoked in past 24 hours from subject's diary (e.g. Day 1).
3. Assess for AEs at time of visit and record.
4. Vital signs, including weight.
5. Review medication packs for compliance.
6. Provide subject with behavioral support information that includes counseling ([Appendix 7](#)). NOTE: it should be stressed to subjects that even if they are smoking less, they must maintain their dosing schedule throughout the Treatment Period.
7. Blood for hematology and serum chemistry testing.
8. Remind subject of their appointment time for the following day and that they must bring with them all study medication packs.

Treatment Day 3

1. Subject to complete the short form of the Tobacco Craving questionnaire ([Appendix 4](#)).
2. Review diary to verify dosing up to time of visit. Review number of cigarettes smoked in past 24 hours from subject's diary (e.g. Day 2).
3. Assess for AEs and any changes to concomitant medications at the clinic visit.
4. Vital signs, including weight.

5. Review medication packs #1 and #2 for compliance and collect pack #1 (which should be empty, as it contained medication for days 1-2). Distribute pack #3 (for Days 5-7).
6. Provide subject with behavioral support information that includes counseling ([Appendix 7](#)). NOTE: it should be stressed to subjects that even if they are smoking less during the study treatment, they must maintain their dosing schedule throughout the Treatment Period.
7. Blood for hematology and serum chemistry testing.
8. Remind subject of their Day 6 appointment date and time and that they must bring with them all study medication packs.

Treatment Day 6 (±1 day)

1. Reconfirm quit date on planned Treatment Day 5, 6, or 7
2. Subject to complete the short form of the Tobacco Craving questionnaire ([Appendix 4](#)).
3. Review diary to verify dosing up to time of visit. Review number of cigarettes smoked in past 24 hours from subject's diary for each daily input (e.g. Days 3, 4 and 5).
4. Assess for AEs and any changes to concomitant medications at the clinic visit.
5. Vital signs, including weight.
6. Review medication packs #2 and #3 for compliance and collect pack #2 (which should be empty, as it contained medication for Days 3-4). Distribute packs #4 and #5 (for Days 8-10 and 11-13).
7. Provide subject with behavioral support information that includes counseling ([Appendix 7](#)). NOTE: it should again be stressed to subjects that even if they are smoking less, they must maintain their dosing schedule throughout the Treatment Period.
8. Blood for hematology and serum chemistry testing.
9. Remind subject of their Day 12 appointment date and time and that they must bring with them all study medication packs.

Treatment Day 12 (±1 day)

1. Subject to complete the short form of the Tobacco Craving questionnaire ([Appendix 4](#)) and the HADS questionnaire ([Appendix 5](#)).
2. Review diary to verify dosing up to time of visit. Review number of cigarettes smoked in past 24 hours from subject's diary for each daily input (e.g. Days 6, 7, 8, 9, 10, and 11).
3. Assess for AEs and any changes to concomitant medications at the clinic visit.
4. Vital signs, including weight.
5. 12-lead ECG.
6. Review medication packs #3, #4 and #5 for compliance and collect packs #3 and #4 (which should be empty, as they contained medication for Days 5-7 and 8-10). Distribute packs #6 and #7 (for days 14-15 and 16-17).

7. Provide subject with behavioral support information that includes counseling ([Appendix 7](#)). NOTE: it should be stressed to subjects that even if they are smoking less, they must maintain their dosing schedule throughout the Treatment Period.
8. Blood for hematology and serum chemistry testing.
9. Remind subject of their Day 16 appointment date and time and that they must bring with them all study medication packs.

Treatment Day 16 (±1 day)

1. Subject to complete the short form of the Tobacco Craving questionnaire ([Appendix 4](#)).
2. Review diary to verify dosing up to time of visit. Review number of cigarettes smoked in past 24 hours from subject's diary for each daily input (e.g. Days 12, 13, 14, and 15).
3. Assess for AEs and any changes to concomitant medications at the clinic visit.
4. Vital signs, including weight.
5. Review medication packs #5, #6 and #7 for compliance and collect packs #5 and #6 (which should be empty, as they contained medication for Days 11-13 and 14-15). Distribute pack #8 (for days 18-21).
6. Provide subject with behavioral support information that includes counseling ([Appendix 7](#)). NOTE: it should be stressed to subjects that even if they are smoking less, they must maintain their dosing schedule throughout the Treatment Period.
7. Blood for hematology and serum chemistry testing.
8. Remind subject of their Day 20 appointment date and time and that they must bring with them all study medication packs.

Treatment Day 20 (±1 day)

1. Subject to complete the short form of the Tobacco Craving questionnaire ([Appendix 4](#)).
2. Review diary to verify dosing up to time of visit. Review number of cigarettes smoked in past 24 hours from subject's diary for each daily input (e.g. Days 16, 17, 18, and 19).
3. Assess for AEs and any changes to concomitant medications at the clinic visit.
4. Vital signs, including weight.
5. Review medication packs #7 and #8 for compliance and collect pack #7 (which should be empty, as it contained medication for Days 16-17). Distribute final pack #9 (for Days 22-25).
6. Provide subject with behavioral support information that includes counseling ([Appendix 7](#)). NOTE: it should be stressed to subjects that even if they are smoking less, they must maintain their dosing schedule throughout the Treatment Period.
7. Blood for hematology and serum chemistry testing.
8. Remind subject of their End of Treatment (Day 27 ±2 days) appointment date and time and that they must bring with them all study medication packs.

Day 27 End of Treatment Visit (± 2 day)

1. Subject to complete the SBQ-R questionnaire ([Appendix 1](#)), the short form of the Tobacco Craving questionnaire ([Appendix 4](#)) and the HADS questionnaire ([Appendix 5](#)).
2. Collect the completed diary from subject. Review diary to verify dosing up to time of visit. Review number of cigarettes smoked in past 24 hours from subject's diary for each daily input (e.g. Days 20, 21, 22, 23, 24, and 25).
3. Assess for AEs and any changes to concomitant medications at the clinic visit.
4. Vital signs, including weight.
5. 12-lead ECG.
6. Review medication packs for compliance and collect packs #7, #8 and #9 (which should be empty, as it contained medication for Days 16-17, 18-21 and 22-25). All used packs must be collected and available for final accountability by the study monitor.
7. Provide subject with behavioral support information that includes counseling ([Appendix 7](#)).
8. Blood for hematology, serum chemistry and cotinine testing.
9. Expired CO.
10. Remind subject that although their treatment is now complete, it is critical to provide the required weekly visits during the follow-up assessment period (Weeks 5, 6, 7 and 8). Schedule date and time for their Week 5 visit.

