6.5. Key Study Endpoints

Achieve has identified the following endpoints as key study endpoints:

- Percent of expected cigarettes smoked (primary efficacy endpoint, see [Section 4.1.1](#))
- Abstinence from Week 5 to Week 8 (other efficacy endpoint, see [Section 4.1.2](#))
- Adverse events (serious adverse events, adverse events that resulted in dose reduction or discontinuation of study drug, all adverse events)

- Exposure to study drug, including study drug compliance

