9.2. Study Drug Compliance

A dose of study drug consisted of 2 tablets. Subjects assigned to the 25-day commercial schedule will be prescribed a total of 100 doses of study drug. Subjects assigned to the tid schedule will be prescribed a total of 69 doses.

Each dose of study drug taken by the subject will be recorded in a subject diary. For each dosing day (Day 1 to Day 25), the dosing date will be recorded as well as each of the dosing times and, for each dosing time, whether the dose was taken by the subject or missed. The total dose of study drug taken over the 25-day treatment period will be derived for each subject.

The following variables will be summarized by treatment arm for the Safety Analysis Set:

- total dose of study drug,
- total number of missed doses,
- percentage of doses missed: $(\# \text{ missed doses} / \# \text{ doses prescribed}) * 100$
- study drug compliance: $[(\# \text{ doses prescribed} - \# \text{ missed doses}) / \# \text{ doses prescribed}] * 100$.

Compliance with study drug will be summarized both as a continuous variable and as a categorical variable (<80%, 80-<90%, 90-<100%, 100%). In addition to summary tables, details of study drug administration and compliance will be listed. The listing will include the total number of doses taken by the subject, total number of doses missed, percentage of doses missed, and percentage of doses taken (i.e. compliance with study drug) in addition to the details of each dose (date of administration, time of administration and whether dose was taken or missed).

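### A Day 16 visit held on Day 15, which its window allows, collects pack #6, the only pack with that day's doses

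*Protocol*

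**What the plan says.** The visit heading in Protocol Section 12.2.3 is "Treatment Day 16 (±1 day"), and Table 10 gives the same window. Day 15, 16 or 17 is therefore allowed.

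At the preceding Day 12 visit the instruction is "Distribute packs #6 and #7 (for days 14-15 and 16-17"). At the Day 16 visit, step 5 tells staff to "collect packs #5 and #6 (which should be empty, as they contained medication for Days 11-13 and 14-15") and to hand out pack #8, for Days 18-21. The subject already holds pack #7.

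Section 9.8 describes the contents: "Each of the 9 packs will contain the correct number of tablets for the days of treatment as follows". The layout is the same for both schedules, and no day appears in two packs. Section 9.6 gives the aim: "study drug will be packaged into folded packets covering treatment segments that will align with clinic visits".

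For compliance, Protocol Section 11 has staff reconcile packs against the diary, "recording the number of tablets taken and the number of missed tablets". SAP Section 9.2 records for each dosing time "whether the dose was taken by the subject or missed". SAP Section 6.5 lists "Exposure to study drug, including study drug compliance" among the key study endpoints.

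**The concern.** Step 5 is written for the nominal Day 16, when pack #6 has been used up. On Day 15 that pack is still in use. If staff follow the step as written, the subject leaves with tablets for Days 16-17 and 18-21 and none for the rest of Day 15. Those doses are either missed or taken from a pack filled for other days, which only moves the shortfall.

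What is at stake is treatment delivery and the compliance record. A dose removed with the pack is recorded as missed, although the procedure, not the subject, caused it. SAP Section 9.2 reports 100% as a category of its own, so one such dose changes how the subject is classified. The Protocol synopsis also says the trial is meant to try out the logistics planned for Phase 3, including compliance with blister packaging. A collection step that can itself remove doses bears on that aim and could be carried into Phase 3.

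**Working it through.** **Prescribed doses.** SAP Section 9.2 states 100 (commercial) and 69 (tid). From the dosing tables in Protocol Section 9.7:

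- Commercial: 3×6 + 9×5 + 4×4 + 4×3 + 4×2 + 1×1 = 18 + 45 + 16 + 12 + 8 + 1 = 100.
- tid: 20×3 + 4×2 + 1×1 = 60 + 8 + 1 = 69.

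Both figures reproduce. Day 15 carries 4 doses on the commercial schedule and 3 on tid.

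**Collection margins.** Margin = earliest allowed visit day − last day covered by the pack collected. Pack days are from Section 9.8; windows and collection steps are from Section 12.2.3.

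| Visit | Earliest day | Pack collected (last day) | Margin (days) |
|---|---|---|---|
| Day 3 | 3 | #1 (2) | 1 |
| Day 6 ±1 | 5 | #2 (4) | 1 |
| Day 12 ±1 | 11 | #3 (7) | 4 |
| Day 12 ±1 | 11 | #4 (10) | 1 |
| Day 16 ±1 | 15 | #5 (13) | 2 |
| Day 16 ±1 | 15 | **#6 (15)** | **0** |
| Day 20 ±1 | 19 | #7 (17) | 2 |

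Before end of treatment, pack #6 is the only one with no margin. At the Day 27 ±2 visit, pack #9 (last day 25) also has margin 25 − 25 = 0, but only one dose is involved.

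**The late side of the windows.** The supply in hand ends exactly on the last allowed day of each next visit: pack #3 on Day 7 (6+1), #5 on Day 13 (12+1), #7 on Day 17 (16+1) and #8 on Day 21 (20+1). The layout was evidently fitted to the windows, so the zero margin for pack #6 looks like an oversight.

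**Effect on compliance.** Compliance = (prescribed − missed) / prescribed × 100 (SAP Section 9.2). Tables 8 and 9 give approximate dosing intervals of 3 hours (commercial, Day 15) and 4-5 hours (tid). Day 15 dosing therefore spans about 3×3 = 9 hours, or 2×4 to 2×5 = 8-10 hours, from the first dose.

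| Timing of the Day 15 visit | Commercial: lost, compliance | tid: lost, compliance |
|---|---|---|
| Before the first dose | 4, 96/100 = 96.0% | 3, 66/69 = 95.7% |
| 2 h after the first dose | 3, 97/100 = 97.0% | 2, 67/69 = 97.1% |
| 7 h after the first dose | 1, 99/100 = 99.0% | 1, 68/69 = 98.6% |
| After the last dose | 0, 100% | 0, 100% |

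These values assume that every other dose is taken and that pack #6 is in fact removed.

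**The case against.** The best defence is that the step is about spent packs. It gives emptiness as the ground for collection, and Section 9.8 speaks of retaining packs that have been used. Step 2 of the same visit checks dosing only up to the time of the visit, so staff know doses may be outstanding. Step 6 tells them to stress keeping to the dosing schedule. Subjects bring all packs to every visit, so a pack left on Day 15 would come back on Day 20 without a new rule. Read together, these make it likely that sensible staff would leave a live pack behind. The Study Procedure Manual, which is not available here, may also cover the case.

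Much of this stands. It makes actual loss less likely, and it means the compliance figures apply only under conditions: a visit on Day 15, a dose still due, and a pack removed although not empty. It does not remove the defect. The remark about emptiness is an expectation derived from the pack days. It can be relied on for Days 16 and 17 but not for Day 15, and no text says what to do when it fails. Sites could reasonably act differently.

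It is also fair to say that an end-of-treatment visit on Day 25 has the same zero margin, so pack #6 is not unique across the whole study. And a general statement that packs align with visits does not promise a gap on every day of every window.

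**Conclusion.** The concern holds: the step is wrong as written for one allowed visit day, and the error is minor. The overlap itself follows from the visit window and the pack table and needs no outside assumption. The loss of doses depends on staff following the step literally while doses are still due.

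For an affected subject the cost is at most 4 of 100 or 3 of 69 doses, about 4.0% and 4.3%, so the two schedules are hit about equally. The documents do not say how often the visit falls on Day 15, so no trial-level figure can be given. Compliance is summarised by arm and does not define an analysis set. The primary endpoint, the percentage of expected cigarettes smoked, is not threatened.

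**What to change.** Add one sentence to step 5 of the Day 16 visit: a pack is not collected while it still covers doses due that day; on a Day 15 visit, pack #6 stays with the subject and is collected at the Day 20 visit. Visits on Day 16 or 17 stay as they are. Optionally, state that an end-of-treatment visit on Day 25 takes place after that day's single dose.

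The cost is one sentence in one visit procedure and, for subjects seen on Day 15, one pack returned a visit later. Visit windows, packaging, dosing and analysis are unchanged, and prescribed doses remain 100 and 69.
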